3.2 Sample Size

In Part A, at least 3 subjects are planned for enrollment into each cohort, with the goal of determining the MTD and/or RP2D of AMG 340. Approximately 60 subjects are anticipated in Part A; however, the total number of subjects in Part A will depend upon the occurrence of DLT events and how dose escalation progresses. If the unknown true toxicity rate/DLT rate is 33% in a given cohort, at least 2 DLTs are likely to be observed.

[figure not shown]
In Part B, up to 40 subjects will be enrolled to further evaluate safety and tolerability, to explore activity of AMG 340 and to evaluate the relationship between PD markers and PK, safety and clinical response. A sample size of 40 subjects was selected to achieve 92% power for testing the hypothesis on ORR at 1-sided alpha of 0.1 using the binomial exact test.

4. Covariates and Subgroups

4.1 Planned Covariates

Not applicable for this study.

4.2 Subgroups

5. Definitions

5.1 Study Endpoints

5.1.1 Primary Endpoints Definitions

Treatment-Emergent Adverse Event (TEAE):

Events categorized as Adverse Events (AEs) starting on or after the first dose of AMG 340 as determined by “Did event start before first dose of AMG 340” equal to “No” or missing on the **Adverse Events** eCRF and up to and including 90 days after the last dose of AMG 340 (however, if subject start a new line of therapy before 90 days follow-up visit, safety follow-up will be performed through 30 days post last dose of AMG 340 or until subject begins a new line of therapy, whichever occurs later) excluding events reported after End of Study Date. **Events that are directly related to metastatic castrate-resistant prostate carcinoma cancer or disease progression (including, but not limited to, preferred terms “prostate cancer”, “progression of prostate cancer”, “prostate cancer metastatic”, “disease progression” etc.) will be excluded from TEAE analysis.**

Treatment-Related Adverse Event (TRAЕ):

A treatment-related AE is any treatment-emergent AE with the relationship flag on the **Adverse Events** eCRF indicating there is a reasonable possibility that the event may have been caused by AMG 340. In the unlikely event that the relationship is missing, the treatment-emergent event will be considered treatment-related and documented in a footnote of the treatment-related summary.

Dose-limiting Toxicities (DLTs):

Investigators determine whether a TEAE qualifies as a DLT per the definition described in protocol section 6.2.1.4.1. For an adverse event to qualify as DLT, the start date must be within 21 days from the date of first dose of AMG 340.

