##### **6.2.1.4 Toxicity Management**

For the purpose of medical management, all adverse events and laboratory abnormalities that occur during the study must be evaluated by the investigator. The table of clinical toxicity grades from the NCI-CTCAE, Version 5.0 (available on CTEP home page: <http://ctep.info.nih.gov>) is to be used in the grading of adverse events and laboratory abnormalities that are reported as adverse events, each of which will be followed to satisfactory clinical resolution, except for CRS and NT which will be graded according to Lee et al (2019). AMG 340 has not been tested clinically in humans, so the adverse event profile in humans is not known.

Adverse events should be classified as pre-existing or as treatment-emergent adverse events:

- A treatment-emergent adverse event is defined as an adverse event not present prior to initiation of AMG 340 treatment, or an adverse event present prior to AMG 340 initiation that worsens in intensity and/or frequency after initiation of AMG 340 treatment.
- A pre-existing adverse event is an adverse event that does not meet these criteria. Subjects with pre-existing adverse events should be assessed for any underlying illness or other causes and treated as appropriate.

Subjects with treatment-emergent adverse events should also be assessed for intercurrent illness or other causes and treated as appropriate. If a treatment-emergent adverse event is unequivocally due to a subject's underlying malignancy or other extraneous cause, dosing with AMG 340 may be modified at the discretion of the Principal Investigator, following discussion with the Medical Monitors. If a treatment-emergent adverse event is not unequivocally due to the subject's underlying malignancy or other extraneous cause, regardless of whether there is a 'reasonable possibility' that the treatment-emergent adverse event is AMG 340-related, the dose of AMG 340 should be modified as follows:

- For subjects who have completed cycle 1 and have at least clinically or radiographically stable disease (SD, MR, PR or CR) but have experienced a reversible treatment-emergent adverse event, the dose of study drug can be delayed for up to 14 days after the scheduled dosing date. A subject for whom dosing is delayed > 14 days should be discontinued from the study.

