##### 9.4.2.3.2 Adverse Events

Subject incidence of all treatment-emergent adverse events will be tabulated by system organ class and preferred term. Tables of fatal adverse events, serious adverse events, adverse events leading to discontinuation from investigational product or other protocol-required therapies will also be provided.

A subgroup analysis of safety with CRS outcomes and PK will be performed for subjects who were administered siltuximab.

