

• Any abnormal laboratory test results (hematology, clinical chemistry, or urinalysis) or other safety assessments (eg, ECG, radiological scans, vital signs measurements), including those that worsen from baseline, that are considered clinically significant in the medical and scientific judgment of the investigator (ie, not related to progression of underlying disease).

• Exacerbation of a chronic or intermittent preexisting condition including either an increase in frequency and/or intensity of the condition.

• New conditions detected or diagnosed after study treatment administration even though it may have been present before the start of the study.

• Signs, symptoms, or the clinical sequelae of a suspected drug-drug interaction.

• Signs, symptoms, or the clinical sequelae of a suspected overdose of either study treatment or a concomitant medication. Overdose per se will not be reported as an adverse event/serious adverse event unless it is an intentional overdose taken with possible suicidal/self-harming intent. Such overdoses are to be reported regardless of sequelae.

• For situations when an adverse event or serious adverse event is due to mCRPC report all known signs and symptoms. Death due to disease progression in the absence of signs and symptoms should be reported as the primary tumor type (eg, metastatic pancreatic cancer). Note: The term “disease progression” should not be used to describe the adverse event.

• “Lack of efficacy” or “failure of expected pharmacological action” per se will not be reported as an adverse event or serious adverse event. Such instances will be captured in the efficacy assessments. However, the signs, symptoms, and/or clinical sequelae resulting from lack of efficacy will be reported as adverse event or serious adverse event if they fulfill the definition of an adverse event or serious adverse event.

Events NOT Meeting the Adverse Event Definition

• Medical or surgical procedure (eg, endoscopy, appendectomy): the condition that leads to the procedure is the adverse event.

- Situations in which an untoward medical occurrence did not occur (social and/or convenience admission to a hospital).
- Anticipated day-to-day fluctuations of preexisting disease(s) or condition(s) present or detected at the start of the study that do not worsen.

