## Recording Adverse Events and Serious Adverse Events

### Adverse Event and Serious Adverse Event Recording

- When an adverse event or serious adverse event occurs, it is the responsibility of the investigator to review all documentation (eg, hospital progress notes, laboratory, and diagnostics reports) related to the event.
- The investigator will then record all relevant adverse event/serious adverse event information in the Events case report form (CRF).
- The investigator must assign the following mandatory adverse event attributes:
  - Adverse event diagnosis or syndrome(s), if known (if not known, signs or symptoms);
  - Dates of onset and resolution (if resolved);
  - Did the event start prior to first dose of investigational product
  - Assessment of seriousness;
  - Severity (or toxicity defined below);
  - Assessment of relatedness to investigational product(s), other protocol-required therapies, and/or study-mandated activity and/or procedures, including [REDACTED] and F-FDG
  - Action taken; and
  - Outcome of event.
- If the severity of an adverse event worsens from the date of onset to the date of resolution, record a single event for each increased level of severity on the Event CRF.
- It is not acceptable for the investigator to send photocopies of the subject's medical records to sponsor/responsible contact research organization (CRO) in lieu of completion of the Events CRF page.
- If specifically requested, the investigator may need to provide additional follow-up information, such as discharge summaries, medical records, or extracts from the

medical records. In this case, all subject identifiers, with the exception of the subject number, will be blinded on the copies of the medical records before submission to Amgen.

- The investigator will attempt to establish a diagnosis of the event based on signs, symptoms, and/or other clinical information. In such cases, the diagnosis (not the individual signs/symptoms) will be documented as the adverse event/serious adverse event.

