9.6.2 Adverse Events

The Medical Dictionary for Regulatory Activities (MedDRA) version 25.1 or later will be used to code all events categorized as adverse events to a system organ class and a preferred term.

Subject incidence of all treatment-emergent adverse events and treatment-related adverse events will be tabulated by system organ class, preferred term and CTCAE grade. Tables of fatal adverse events, serious adverse events and adverse events leading to withdrawal of AMG 340 by system organ class and preferred term **will be summarized**.

The severity of each adverse event will be graded using CTCAE version 5.0 with the exception of CRS, TLS, and ICANS.

CRS must be graded as per ASTCT referenced by Lee et al, 2019, TLS must be graded using the criteria referenced by Coiffier et al, 2008 and ICANS must be graded by using the criteria referenced by Lee et al, 2019.

The adverse events of interest (CRS) will be summarized by preferred term and worst grade.

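### The SAP drops disease-related events from the TEAE analysis under an open-ended rule that does not protect events flagged as related to AMG 340, so TEAE and TRAE incidence can be understated

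*SAP*

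**What the plan says.** **SAP.** Section 2.1 lists TEAEs and TRAEs among the primary endpoints. Section 5.1.1 defines a TEAE by timing and then adds an exclusion: "Events that are directly related to metastatic castrate-resistant prostate carcinoma cancer or disease progression (including, but not limited to, preferred terms". Four terms follow, each naming prostate cancer or its progression. They are examples only, and the list ends open. Such events "will be excluded from TEAE analysis". The same section then says "A treatment-related AE is any treatment-emergent AE with the relationship flag" for AMG 340, so TRAEs are drawn from TEAEs. A missing relationship is counted as related.

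**Protocol.** Section 6.2.1.4 defines the term by onset or worsening after the start of treatment: "A treatment-emergent adverse event is defined as an adverse event not present prior to initiation of AMG 340 treatment", or one that worsens afterwards. Section 9.4.2.3.2 states the analysis: "Subject incidence of all treatment-emergent adverse events will be tabulated by system organ class and preferred term". Neither contains a disease exclusion. Appendix 4 instructs sites: "For situations when an adverse event or serious adverse event is due to mCRPC report all known signs and symptoms". It also tells them not to use disease progression as an event term, and to report a progression death without signs or symptoms under the tumor type. Finally, Appendix 4 leaves the definition of a TEAE to the SAP.

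**The concern.** Advanced mCRPC and a T-cell engager can produce overlapping clinical pictures, and this trial has no control arm to separate them. If events can be taken out of a primary safety endpoint because they are thought to be disease, the reported profile depends on who makes that call, when, and by what standard. The visible SAP text states none of these.

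The reporting instruction makes the open ending matter. Sites are told to describe mCRPC-caused events by their signs and symptoms, so most such events should arrive as symptom or finding terms outside the four named examples. Whether they stay in the TEAE tables turns entirely on the open part of the rule. An event flagged as related to AMG 340 has no stated protection. If it were judged disease-related, it would leave the TRAE table as well.

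**Working it through.** **1. Can the data settle which events are disease-related?** The mandatory attributes in Appendix 4 include "Assessment of relatedness to investigational product(s), other protocol-required therapies, and/or study-mandated activity and/or procedures". The causality column on the sample SAE form (Figure 11-1) asks about the investigational product or a device, with a separate check box for study procedures. Appendix 4 asks the investigator to weigh underlying disease when assessing causality, but describes no coded item for the result. So no attribute documented in the protocol identifies the excluded class. The Adverse Events eCRF itself is not among the documents.

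**2. Is one standard of attribution used throughout?** No. Protocol Section 6.2.1.4.1 sets aside, for DLT purposes, only events unequivocally due to the malignancy or another extraneous cause. The SAP exclusion asks whether an event is directly related to the disease. These are different thresholds, and the SAP does not connect them.

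**3. Are there borderline events in the plan itself?** Yes. SAP Section 5.1.2 takes symptomatic skeletal events, such as fracture and spinal cord compression, from the Adverse Events eCRF. The SAP does not say whether they stay in the TEAE tables.

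**4. Direction.** Protocol Section 9.4.2.3.1 makes the Safety Analysis Set the default for safety endpoints. Its denominator is all treated subjects, which the exclusion does not change. Removing events can only keep or shrink the set of subjects with at least one qualifying event. TEAE incidence therefore stays the same or falls, and so does TRAE incidence as its subset. It cannot rise.

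**5. Scale.** The nearest stated figure is in Protocol Section 2.2.4.3, reported under a TEAE definition with no disease exclusion: 8 of 23 treated subjects had a grade 3 or higher event.

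- Reproduced: 8/23 = 34.8%.
- One subject: 1/23 = 4.3 percentage points.
- Illustration, where j is the number of those 8 subjects whose every grade 3 or higher event is excluded (an assumption, not an estimate), and the rate is (8 − j)/23:

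| j | Rate |
|---|---|
| 0 | 8/23 = 34.8% |
| 1 | 7/23 = 30.4% |
| 2 | 6/23 = 26.1% |
| 3 | 5/23 = 21.7% |
| 4 | 4/23 = 17.4% |

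The documents give no basis for choosing j, and j = 0 is possible.

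**The case against.** The strongest reply is that the exclusion is ordinary and authorised. Appendix 4 hands the TEAE definition to the SAP, and the definition in Protocol Section 6.2.1.4 sits in a passage on medical management. All four named terms label the cancer or its progression. The instruction on progression deaths means such terms will reach the database, so the rule has a proper target. A natural reading is that only these entries go, and nothing visible says that sign, symptom or laboratory terms will be removed. An event with a reasonable possibility of being caused by AMG 340 is also hard to call directly related to the cancer.

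Most of this stands. The delegation permits an exclusion and makes it doubtful that the SAP has departed from the protocol. It does not supply a boundary. The rule is worded by relation to disease, with the terms only as examples, so the narrow reading is plausible but not what is written.

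A reader might infer more than the documents support:

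- **That DLTs are lost too.** Investigators determine DLTs under Protocol Section 6.2.1.4.1, and the SAP gives them their own table and analysis set. Appendix 3 has the dose level review use all available study data, not these tables.
- **That serious and fatal events are hit hardest.** SAP Section 9.6.2 applies the words "treatment-emergent adverse events" to the overall incidence tables, but does not label the fatal, serious and withdrawal tables that way. Whether the exclusion reaches them is unclear.
- **That no form captures relation to disease.** The eCRF is unavailable, and SAP Section 5.1.2 mentions event categories for Part B that Appendix 4 does not list.
- **That terms will be chosen after results are seen.** Protocol Section 9.4 has the SAP finalized before database lock. The list is unspecified, which is not the same as post hoc.

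**Conclusion.** The point holds as a gap in pre-specification that affects a primary safety endpoint. As written, SAP Section 5.1.1 allows TEAE incidence, and TRAE incidence with it, to be lowered by a judgement whose scope, owner and timing are not stated, on open-label data with no comparator. The direction is certain: never upward. The size cannot be computed from the documents. It could be nil if only disease-name terms are removed, and each subject leaving the interim grade 3 or higher count would move it by 4.3 points.

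One could go further and subtract every interim grade 3 anemia (3), hydronephrosis (1) and failure to thrive (1) from the 8 subjects, giving 3/23 = 13.0%. That is not supportable. It needs five different subjects with no other grade 3 or higher event. The other three would then have to carry all the remaining grade 3 events in Protocol Section 2.2.4.3, the grade 4 neutropenia and thrombocytopenia, and the fatal hemorrhage. Nothing suggests that any of the five events would be excluded.

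The conclusion rests on the visible SAP text and on the event attributes documented in the protocol. An eCRF field for relation to disease would make the judgement traceable, but would not close the list or protect events flagged as related.

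**What to change.** Amend SAP Sections 5.1.1 and 9.6.2 before database lock:

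1. Replace the open wording with a closed list of preferred terms that only name prostate cancer or its progression, fixed before database lock.
2. State that sign, symptom and laboratory terms are never excluded, nor is any event flagged as related to AMG 340 or recorded as a DLT.
3. Provide an all-TEAE table without the exclusion.
4. List every excluded event with its grade, seriousness and relatedness.
5. State whether the exclusion applies to the fatal, serious and withdrawal tables.

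The cost is some SAP wording, a few extra tables and one listing. The downside is that the all-TEAE table will contain some events that are purely progression. The listing lets a reader identify them.

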## 1.3 Schedule of Activities (SoA)

Table 1-1. Schedule of Activities

Study Activity	Screening	C1 Treatment Period DLT Window (Days 1-21)										Treatment Period (3-week cycles)								UNS Visit a	EOT b	SFU n	Survival FU/LTFU o				
		W1					W2 d			W3		C2		C3			C4 & C5		C6		C7+						
		D1	D2	D3	D5	D6	D7	D8	D9	D10	D15	D1	D15	D1	D8	D15	D1	D1	D2	D15	D1						
Study Day	Day -28 to Day -1																					Within 30d after last dose	90d after last dose	Every 6 months			
Window				±1h	±1h	±1d	±1h	±1h	±1d	±1h	±1h	±1d	±1d	±1d	±1d	±1d	±1d	±1d	±1d	±1d							
Informed Consent	X																					+7d	±7d				
Incl/Excl Criteria	X	X																									
Inpatient Stay c		X	X	X	X c	X c	X c	X c	X c	X c																	
Demographics, Medical & Cancer History, Height	X																										
Complete Physical Exam	X																					X	X				
Symptom-directed Physical Exam		X	X	X	X	X i	X i	X	X k	X k	X	X	X	X	X	X	X	X	X	X	X	X	X				
Weight	X	X																									
Vital Signs d	X	X	X	X	X	X i	X i	X	X k	X k	X	X	X	X	X	X	X	X	X	X	X	X	X	X			
ECHO	X																										
12-Lead ECG	X																										
ECOG Performance Status	X	X																				X	X	X	X		
Clinical Chemistry and Hematology e	X	X	X	X	X	X i	X i	X	X k	X k	X	X	X	X	X	X	X	X	X	X	X	X	X	X			
Coagulation Panel e	X																										
Urinalysis	X																										
Viral Screen	X																										
Testosterone	X																										
AMG 340 administration f		X		X		X j						X	X	X	X	X	X	X	X	X	X						
Anti-AMG 340 antibody e																											

Refer to

Study Activity	Screening	C1 Treatment Period DLT Window (Days 1-21)										Treatment Period (3-week cycles)							UNS Visit a	EOT b	SFU n	Survival FU/LTFU o			
												C2			C3			C4 & C5							
		W1			W2 d			W3			W1	W3	W1	W2	W3	W1	W1	W3	W1	Within 30d after last dose	90d after last dose	Every 6 months			
Study Day	Day -28 to Day -1	D1	D2	D3	D5	D6	D7	D8	D9	D10	D15	D1	D15	D1	D8	D15	D1	D1	D2	D15	D1	UNS Visit a	EOT b	SFU n	Survival FU/LTFU o

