#### **6.2.1.2 Dose Priming**

Based on the nonclinical pharmacology of AMG 340, a lower rate of CRS is anticipated than with other T-cell-engaging bispecifics; however, based on the mechanism of action of AMG 340, the most likely DLT to occur is still CRS  $\geq$  grade 3. Cytokine release syndrome will be managed per Principal Investigator discretion and institutional guidelines (a guide for management of CRS is provided in [Table 6-6](#) if institutional guidelines have not been established). Definitions for adverse events, serious adverse events, and DLTs are provided in Section [8.4.6.1.1](#), [8.4.6.1.2](#), and [6.2.1.4.1](#), respectively.

If a grade  $\geq$  3 CRS event occurs in Cohort N (where N represents a Cohort number) during the DLT period, or at the discretion of the DLRT, a dose equal to or less than the dose for Cohort N will be designated as the ‘Priming Dose’ and dose administration in subsequent cohorts (Cohorts N+1 and on) may be modified as follows:

- On Cycle 1 Day 1, subjects will receive the Priming Dose.
- On Cycle 1 Day 8, subjects will receive the full dose corresponding to the cohort in which they have been enrolled.

Note: a second priming dose may be introduced based on emerging data.

If a subject experiences CRS grade  $\geq$  2, or any other grade  $\geq$  2 toxicity after receiving a priming dose that is not unequivocally due to the subject’s underlying malignancy or other extraneous cause, administration of the full dose on cycle 1 day 8 must await approval by the Amgen Medical Monitor(s). At a minimum, CRS must have resolved to

grade  $\leq$  1 before the next is administered. The dose and timing of the full dose for such a subject may be modified at the discretion of the Amgen Medical Monitor and the Investigator; if the subject has their full dose reduced in cycle 1, the subject will be considered DLT-unevaluable and should be replaced. In subsequent cycles, subjects will receive the full dose on day 1.

Following implementation of a priming dose, if administration of the full dose is delayed in cycle 1, the DLT period for that subject should be extended to the same degree (eg, if the full dose is delayed by 4 days, the DLT period will also be extended 4 days). For clarity, treatment-emergent adverse events meeting criteria for a DLT will be treated as a DLT whether they occur after administration of the priming or the full dose.

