- During any cycle, if a subject develops an ANC < 500/ $\mu$ L, platelets < 10,000/ $\mu$ L, or a hemoglobin < 6.5 g/dL, blood samples must be collected every 3 days and study treatment withheld. Treatment may resume when ANC returns to  $\geq$  1,000/ $\mu$ L, platelet counts return to  $\geq$  50,000/ $\mu$ L or baseline platelet count levels (in subjects with baseline platelets < 50,000/ $\mu$ L), or hemoglobin returns to  $\geq$  8.0 g/dL.
- AMG 340 should be discontinued in any subject who experiences CRS, TLS, or a non-hematologic treatment-emergent adverse event that meets DLT equivalent criteria until resolution of the toxicity to  $\leq$  grade 1 or baseline; thereafter study drug may be resumed with one dose level reduction with Medical Monitor approval.

Up to 2 dose reductions are allowed to manage toxicity; thereafter toxicity will be deemed 'unacceptable' and the subject will be discontinued from therapy. Assessment schedules and cycles are fixed and should continue regardless of whether a dose is held.

While investigator discretion should be used for subject management with regards to toxicities, guidelines for management of CRS and NT are provided in [Table 6-6](#) and [Table 6-5](#).

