#### **6.2.1.4.1 Dose Limiting Toxicity Definition for Dose Escalation**

The DLT observation period for dose escalation purposes is 21 days and covers the first complete treatment cycle of AMG 340 (1 dose of AMG 340; or up to 3 doses if priming has been implemented). Regular teleconferences will be conducted among the DLRT to examine/confirm potential DLTs, assess adverse events, and evaluate laboratory abnormalities. Events occurring outside the DLT window may be evaluated during these calls when making dose escalation decisions. A DLT is defined as a treatment emergent adverse event that is not unequivocally due to the subject's underlying malignancy or other extraneous cause and meets the criteria below.

The NCI-CTCAE version 5.0 will be used. DLT definitions are provided below.

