#### **6.2.1.6.1.2 Miscellaneous Dose-limiting Toxicity**

Any toxicity thought to be related to the study drug that, at the discretion of the investigator, is thought to warrant withholding the drug. Other adverse events may be considered a DLT as determined by the Medical Monitor, in conjunction with the investigator.

All decisions regarding continued dosing for individual subjects will be medically managed by the investigator, in conjunction with the Medical Monitor(s), as appropriate. These decisions will be driven by the DLT criteria as described above.

Any subject who does not complete the full 21-day DLT observation period for any reason other than DLT will be considered non-DLT-evaluable for dose escalation and/or MTD assessment and will be replaced at the same dose level. Additional subjects may be enrolled at a given dose level in the absence of DLT to explore factors influencing adverse events or to accumulate additional safety data.

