##### **Infusion Delay due to Technical/Logistical Issues**

If the infusion delay was  $\leq$  7 days, the dose can be administered without specific precautions. Procedures performed will follow the schedule of assessments for the cycle day on which the infusion was originally planned. The following infusion should then be administered after 21 ( $\pm$  1) days (eg, if the day 8 infusion needs to be delayed for logistical issues, and could only be administered on day 10, the next infusion should be administered 21 days later [ $\pm$  1 day]). The  $\pm$  1-day window is allowed until the original dosing schedule is met again.

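### The SAP's fixed 21-day DLT cut-off omits the protocol's extension for a delayed cycle 1 full dose, and its readable text does not declare the difference

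*SAP*

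**What the plan says.** **SAP.** Section 5.1.1 leaves it to the investigator to judge whether an event is a DLT under Protocol 6.2.1.4.1. It then adds a separate timing condition: "the start date must be within 21 days from the date of first dose of AMG 340". It does not refer to Protocol 6.2.1.2. Table 9-3 tabulates the subject incidence of DLTs by planned dose level.

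**Protocol, general rule.** Section 6.2.1.4.1: "The DLT observation period for dose escalation purposes is 21 days and covers the first complete treatment cycle of AMG 340". Section 6.2.1.6.1.2 uses the same length for evaluability: "Any subject who does not complete the full 21-day DLT observation period for any reason other than DLT will be considered non-DLT-evaluable". The column heading in Table 1-1 also gives days 1 to 21. None of these places mentions an extension.

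**Protocol, rule for primed subjects.** Section 6.2.1.2 places the full dose on cycle 1 day 8 and states that, once priming has been implemented, "if administration of the full dose is delayed in cycle 1, the DLT period for that subject should be extended to the same degree". Its example is a 4-day delay with a 4-day extension. Section 2.2.4.3 reports that a grade 3 CRS event in cohort 5 led to a priming dose being introduced, so the rule applies to this trial.

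**Declared changes.** The SAP is written for protocol amendment 5, the version that contains this rule. The readable text of SAP section 10 lists two changes: one on adverse events related to other required therapies, the other on combining the primary and final analyses. Neither concerns the DLT period.

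**The concern.** DLT is the endpoint for the primary objective of finding the MTD or RP2D. The extension in Protocol 6.2.1.2 gives a subject whose full dose is late the same observation time at that dose as everyone else. The SAP's cut-off runs from the first dose, which under priming is the priming dose, so each day of delay removes a day of counted follow-up at the full dose. Delays are foreseeable: after a grade 2 or higher toxicity following priming, Protocol 6.2.1.2 makes the full dose wait for Medical Monitor approval, and Protocol 6.2.2.4 covers logistical delays. What is at stake is a final table for a primary endpoint that disagrees, without saying so, with the DLT counts that the protocol's own rule produces.

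**Working it through.** The 21 days is a definition, so there is no power or alpha figure to reproduce. The check is day arithmetic.

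**Inputs**
- Planned full-dose day under priming: day 8 (Protocol 6.2.1.2).
- DLT period without delay: days 1 to 21 (Protocol 6.2.1.4.1 and Table 1-1).
- Delay d: 4 days (the example in Protocol 6.2.1.2) and 2 days (the example in Protocol 6.2.2.4, "if the day 8 infusion needs to be delayed for logistical issues, and could only be administered on day 10").
- Last day counted by the SAP, L: day 21. If the day of the first dose is taken as zero, the wording also permits day 22.

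**Formulas**
- Full-dose day: F = 8 + d.
- Protocol end of DLT period: E = 21 + d.
- Protocol days from the full dose: E − F + 1 = 14 for every d.
- SAP days from the full dose: L − F + 1, which is 14 − d for L = 21 and 15 − d for L = 22.

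| Delay d | Full dose F | Protocol end E | Protocol days | SAP days of those 14, L = 21 | SAP days of those 14, L = 22 |
|---|---|---|---|---|---|
| 0 | day 8 | day 21 | 14 | 14 | 14 (day 22 lies outside the protocol period) |
| 2 | day 10 | day 23 | 14 | 12 | 13 |
| 4 | day 12 | day 25 | 14 | 10 | 11 |

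With no delay and L = 21 the two documents agree. In the 4-day example, onsets on days 22 to 25 (or 23 to 25) are DLTs under Protocol 6.2.1.2 but not under SAP 5.1.1. That is 4/14 = 28.6% (or 3/14 = 21.4%) of the observation days from the full dose. These are shares of days, not of DLTs.

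**Direction.** Suppose x of n evaluable subjects have a DLT and one of them has an onset only in the extension. The reported incidence becomes (x − 1)/n if that subject stays in the analysis set, or (x − 1)/(n − 1) if he leaves it. The first is below x/n. The second is no higher than x/n, because n(x − 1) ≤ x(n − 1) reduces to x ≤ n. So omitting the extension never raises the incidence. The day-22 reading is a separate and smaller matter: it would add one day for undelayed subjects, in the opposite direction.

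**The case against.** The strongest reply is that the SAP follows the section that defines a DLT. Protocol 6.2.1.4.1 says 21 days, as do 6.2.1.6.1.2 and Table 1-1, and the exception sits in the dose-priming section. This stands in part: the protocol does not cross-refer to its own extension, and that gap is as much a cause as the SAP. It does not rescue the SAP wording. Section 6.2.1.2 is the specific rule for primed subjects, and the SAP makes its cut-off mandatory, so it can strike out an event that the investigator has called a DLT.

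It can also be said that the effect may be very small. That stands. Only a primed subject with a delayed full dose, and with no qualifying event before the extension, is affected. The documents do not report how many full doses were delayed. An excluded event would still appear in the adverse event tables by grade, though not as a DLT.

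Some stronger readings are tempting but not supported:
- *Wrong escalation decisions.* The DLRT works under the protocol, and 6.2.1.4.1 lets it weigh events outside the window.
- *A 7-day worst case.* Protocol 6.2.2.4 says that for logistical delays of up to "7 days, the dose can be administered without specific precautions". That says when no precautions are needed. It is not a maximum, and 6.2.1.2 sets none.
- *The subject certainly stays in the denominator.* Protocol 6.2.1.4 says "Assessment schedules and cycles are fixed and should continue regardless of whether a dose is held", but 6.2.2.4 moves the next infusion after a logistical delay. When cycle 1 is complete is therefore unsettled.
- *A deliberate undisclosed change.* Figures are missing around the SAP section 10 heading in the public copy, so only its readable text can be said to be silent.

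**Conclusion.** The point holds as a conflict over which events are counted. Read literally, SAP 5.1.1 leaves out DLTs that Protocol 6.2.1.2 recognises, and the readable part of SAP section 10 does not say so. This is a stated rule that gives a different count, not a missing detail. In the protocol's 4-day example the SAP covers 10 (or 11) of 14 days from the full dose.

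The effect on the reported incidence is downward or nil, and its actual size is unknown. It depends on how many full doses were delayed and on when DLTs start after the full dose, and the documents give neither. If all such DLTs start early, none is lost. The one subject with reported DLTs had neutropenia and thrombocytopenia, with no onset day given (Protocol 2.2.4.3).

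A secondary conflict lies mainly inside the protocol. Section 6.2.1.2 makes a subject whose cycle 1 full dose was reduced unevaluable for DLT and to be replaced. Protocol 9.3 omits that rule, and SAP 6.3.3 repeats 9.3. A reader might call this a SAP departure too, but the SAP only carries over the protocol's own population definition. The status of a subject with a DLT after priming and then a reduced full dose is also unclear, because 6.2.1.2 counts qualifying events after either dose.

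**What to change.** 1. In SAP 5.1.1, replace the cut-off with: onset within the subject's protocol DLT period (days 1 to 21, plus any extension under Protocol 6.2.1.2). This also settles the last day counted. Alternatively, keep the fixed cut-off and declare it in SAP section 10 as a change from the protocol.
2. Footnote Table 9-3 with the number of subjects whose cycle 1 full dose was delayed.
3. At the next protocol amendment, reconcile 6.2.1.2 with 6.2.1.4.1 and 6.2.1.6.1.2 on the DLT period, and 6.2.1.2 with 9.3 (and SAP 6.3.3) on evaluability after a reduced full dose. Which rule should govern is for the sponsor to decide.

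Items 1 and 2 cost one SAP sentence and one footnote, with no extra patients or procedures. Item 3 involves protocol text, which must go to the IRB/IEC, so it can wait for an amendment that is being made anyway. The SAP correction does not depend on it.
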